8.2.4. Adverse Event Safety Analyses

Adverse events will be coded using the Medical Dictionary for Regulatory Activities (MedDRA) coding dictionary.

The reporting of the CEC-adjudicated CV endpoint events has been described in Section 7.2, Section 8.2.1, and Section 8.2.2. However, AE summaries and analysis will also include the AEs and SAEs associated with the adjudicated events listed below:

- All-cause mortality (CV and non-CV mortality)
- Non-fatal MI
- Non-fatal stroke
- Hospitalization for HF
- Thromboembolic events (vascular access thrombosis, deep vein thrombosis, pulmonary embolism)

200807 | Statistical Analysis Plan Amendment 3 03 Mar 2021 | TMF-11879471 | 2.0

CONFIDENTIAL

200807

For the purpose of AE summaries and analysis, the investigator-reported AE details will be used, regardless of the adjudication outcome of the event.

Adopting recommendations from the Pharmaceutical Research and Manufacturers of America (PhRMA) Safety Planning, Evaluation and Reporting Team (SPERT) [Crowe, 2009], the first two tiers of the three-tier system will be used for the evaluation of AEs to examine the level of statistical evidence for differences between treatment groups.

- Tier 1 events in this study are defined as treatment emergent AEs of special interest (AESI). Tier 1 events will include AEs which meet criteria for inclusion as an AESI (see Section 10.6.4). Statistical comparisons will be made to compare the number and % of AESIs between the treatment groups, using the CMH chi-square test. A nominal statistical association will be declared if the unadjusted two-sided p-value for an event is less than 0.05.
- Tier 2 events in this study are defined as the most common treatment emergent AEs (those occurring in ≥ 5% of subjects in any treatment group). Tier 2 events are mutually exclusive of the Tier 1 AESI events. Any statistical comparisons for Tier 2 events will be made to compare treatment groups with multiplicity adjustment, using a CMH chi-square test, and the double false discovery rate (FDR, see Section 10.6.4) [Mehrota, 2012]. The double FDR multiplicity procedure is designed to limit the number of false positive signals identified to no more than two-sided 10% (the false discovery rate).

Unless otherwise specified, all other AE and SAE summaries will include all AEs.

See Section 10.4.1 for AE treatment state definitions.

The adverse event safety analyses will be based on the Safety population, unless otherwise specified.

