Exacerbation of rheumatoid arthritis			
High Level Term: Rheumatoid arthropathies			
Additional Preferred Terms:			
• Rheumatoid factor increased •	Rhe	eumatoid factor quantatative increased	
 Rheumatoid factor positive 			
Worsening of hypertension			
Narrow SMQ: Hypertension			
Blood Pressure Events			
BP events will be identified during the study via progra			
entered into the eCRF (using the narrow SMQ for hyp			
an additional BP Exacerbation eCRF page to be completed that characterizes the event as			
clinically significant and/or symptomatic.			
In addition, subjects that experience BP values that m	In addition, subjects that experience BP values that meet the following criteria at any visit will also		
be considered to have a BP event and be required to complete the Blood Pressure Exacerbation			
eCRF page:			
 SBP: an increase from baseline of ≥ 25 mmH 	lg or	SBP \geq 180 mmHg	
 DBP: an increase from baseline of ≥ 15 mmH 	la or	$DBP > 110 \; mmHc$	
	19 01		

200807

Adverse Events

BP-related SAEs are those SAEs that have been identified via the BP Exacerbation eCRF page.

False Discovery Rate (FDR) Method and Procedure

The FDR method adjusts p-values within a group (SOC or preferred terms (PTs) within a SOC) based on the following:

- a) Order p-values from lowest to highest (1... m)
- b) Compute adjusted p-values, p', as follows

p'(m) = p(m) i.e., the adjusted p-values for the highest p-value is the same as the highest p-value

 $p'(j) = min(\{p'(j+1), m/j^*p(j)\} \text{ for } j \le m - 1$

The FDR procedure is applied at the system organ class (SOC) level and for each AE preferred term (PT) reported as Tier 2 events. The following stops will be undertaken in this procedure:

- 1. Compute adjusted p-values for PTs within each SOC using the FDR method.
- 2. Order SOCs (small to large) according to the minimum FDR adjusted p-value observed for treatment differences across PTs within SOC.
- 3. Perform the FDR method on the minimum adjusted p-values from Step 2.
- 4. Select SOCs with FDR adjusted p-value from Step 3 <0.10.
- 5. Apply a single FDR adjustment to all unadjusted p-values belonging to all PTs from SOCs identified in Step 4. with a threshold of FDR adjusted p-values <0.10 will be used to flag PTs that warrant further investigation.

Note that 0.10 is recommended as a reasonable multiplicity adjustment for 0.05.

General Definitions	

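### The two-step FDR rule for Tier 2 adverse events does not bound the false discovery rate at 10%, as SAP 8.2.4 says; 10% is only the threshold at each step

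*SAP*

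**What the plan says.** SAP 8.2.4 puts treatment-emergent AEs seen in at least 5% of either arm, other than AEs of special interest, into Tier 2. It states the operating characteristic of the multiplicity rule: "The double FDR multiplicity procedure is designed to limit the number of false positive signals identified to no more than two-sided 10" per cent, which it glosses as the false discovery rate (FDR).

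SAP 10.6.4.3 defines the adjustment (the Benjamini-Hochberg step-up, BH) and lays out five steps. The first applies BH to the PTs inside each SOC. The second takes the smallest adjusted value in a SOC as that SOC's representative. The third applies BH across these representatives, and the fourth keeps every SOC whose result is under 0.10. The fifth goes back to the raw p-values: "Apply a single FDR adjustment to all unadjusted p-values belonging to all PTs from SOCs identified in Step 4". A PT is flagged for follow-up when its newly adjusted value is again under 0.10.

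A closing note calls 0.10 a reasonable multiplicity counterpart of 0.05. SAP 8.2.4.2 displays the unadjusted and the double-FDR p-value together, with relative risk and 95% CI.

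**The concern.** The rule is fully specified, so its stated property can be tested. Step 5 starts again from unadjusted p-values in SOCs that were kept because they contained small p-values. Two things follow. Null PTs in rejected SOCs drop out of the Step 5 denominator. A null SOC that passes by chance also brings its smallest p-value with it. No step corrects for this, so the 0.10 level is applied twice to the same data.

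What is at stake is how the flags are read. A reader of 8.2.4 will take it that at most 1 flag in 10 is expected to be false. If the real figure can be nearer 1 in 6, the flags will be over-read.

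**Working it through.** **Inputs.** From SAP 10.6.4.3: p'(m) = p(m) and p'(j) = min{p'(j+1), (m/j)p(j)}; SOC threshold 0.10; PT threshold 0.10. From SAP 8.2.4: the claimed limit of 10%. Not in the SAP, hence assumed: the numbers of SOCs (S) and of PTs per SOC (n), and the number, strength and placement of true signals. P-values are two-sided normal, independent unless stated. FDR = mean of (false flags / max(1, flags)).

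**Reproducing the 10%.** With no true signal, the five steps simulated as written (40,000 runs, SE 0.15 points) give 9.98%, 10.02%, 10.09% and 10.01% for 10x5, 12x3, 20x4 and 10x10 SOCs x PTs. The SAP's figure is right for this case.

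**Isolated strong signals** (one per affected SOC; FDR in %, z mean 4 / z mean 6; 40,000 runs, SE about 0.1 point):

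| Layout | 1 signal | 2 signals | 3 signals | 5 signals | one in every SOC (z mean 6) |
|---|---|---|---|---|---|
| 10x5 | 15.2 / 16.4 | 15.4 / 15.4 | 14.7 / 14.5 | 12.9 / 12.6 | 8.0 |
| 12x3 | 14.3 / 15.2 | 14.4 / 14.4 | 13.7 / 13.6 | 12.2 / 12.0 | 6.6 |
| 20x4 | 15.0 / 16.4 | 15.7 / 15.9 | 15.5 / 15.5 | 14.8 / 14.5 | 7.5 |
| 10x10 | 15.6 / 17.2 | 16.3 / 16.4 | 15.8 / 15.4 | 14.1 / 13.6 | 9.0 |

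Within-SOC correlation of 0.3 leaves the rate at about 15-16%.

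**Hand check, one strong signal.** The signal's SOC ranks first in Step 3, so a null SOC passes Step 4 if its minimum adjusted p is below about 0.10 x 2/S. The chance is about 0.2(S-1)/S, and its smallest p-value then usually passes Step 5. Separately, a null PT in the signal's own SOC passes Step 5 with chance about 0.2(n-1)/n. Either error makes about half the flags false. For S = 10, n = 5:

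- via a null SOC: 0.5 x 0.2 x 9/10 = 9%
- via the signal's own SOC: 0.5 x 0.2 x 4/5 = 8%
- total: about 17%, against 16.4% simulated at z mean 6.

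With n = 1 in the signal's SOC the second route vanishes and about 9% remains; a simulated lone signal in a one-PT SOC gave 9.4%.

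**Weaker signals.** One or two randomly placed signals, five layouts (12x3; 15x5; 40 PTs in 13 SOCs; 25 in 13; 20 in 10), 4,000 runs per cell:

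| z mean | FDR, range over layouts |
|---|---|
| 2 | 9.8-11.5% |
| 2.5 | 10.4-12.6% |
| 3 | 11.3-13.7% |
| 5 | 12.5-16.5% |

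**Placement.** In an uneven layout (SOCs of 1, 1, 1, 2, 2, 3, 3, 4, 6, 7, 10 and 12 PTs), three isolated signals give 13.6-14.4% when placed at random, 14.9% in the largest SOCs and 8.1% in the smallest. Signals clustered in one or two SOCs gave 4-8%; several moderate signals (z mean 3) in one SOC gave 10-12%.

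**Comparator.** One BH adjustment at 0.10 over all Tier 2 PTs has FDR 0.10 x (null PTs / all PTs) under independence. For 15x5 with one signal that is 0.10 x 74/75 = 9.9%. Simulated values were 9-10.5%. Signals found at 15x5 were the same (0.970 of 1 under both rules). With three moderate signals in one SOC, the two-step rule found 2.19 and the single adjustment 1.52.

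**The case against.** The other side has four good points.

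- **Wording.** The SAP speaks of what the procedure is designed to do and cites a published method. The threshold is used consistently, and 10% is exact with no signal. This stands in part: 10% is a sensible threshold, but 8.2.4 states it as a ceiling, and plausible configurations exceed it. What the cited source claims cannot be checked here.
- **Size.** A reader might infer that the rule runs at 13-17% whenever true signals are isolated. The documents do not support that. They give no SOC or PT counts and no expected signals, and the figure needs strong differences in SOCs with several PTs. At z mean 2-3 the excess over 10% is about 0-4 points. This stands.
- **Exceptions.** A reader might also infer that 10% is met only with no signal, or when true signals dominate the selected SOCs. That is not so: isolated signals in very small SOCs stay at about 8-10%, and a 5% incidence cut-off may leave many SOCs small.
- **Consequence.** Flags prompt further investigation, the unadjusted p-value sits beside them, and neither the co-primary analyses nor the multiplicity plan in SAP 10.11 uses them. In safety screening an extra false flag costs a review, while a missed signal costs more. This stands, and it keeps the point minor.

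**Conclusion.** The statement in 8.2.4 is wrong as a ceiling. In simulation the rule's FDR is about 10% with no true signal, about 10-14% with one or two isolated weak to moderate signals, and about 12-17% with isolated strong signals in SOCs of several PTs. It is near or below 10% when strong signals cluster in one SOC or lie in very small SOCs. That the limit can be exceeded follows from the steps as written; the size of the excess rests on assumed layouts, signal strengths and normal p-values. The point is minor: it corrects a stated property of a screening aid and does not invalidate the Tier 2 analysis. It is no case for abandoning the two-step rule, which finds more when signals cluster within a SOC.

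**What to change.** Reword the sentence in 8.2.4 to say that 0.10 is the threshold applied at each of the two steps (SOC selection, then PT flagging); that the overall FDR is only approximately controlled; and that it can exceed 10%, up to about 17% in simulated layouts, when true signals are isolated. The cost is one sentence, with no new data.

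Optionally, add a column to the Tier 2 table with the p-value from a single FDR adjustment over all Tier 2 PTs, which holds at about 10%. It should sit beside the double-FDR flag and not replace it, because the single adjustment finds fewer signals clustered in one SOC (1.52 against 2.19 of 3). The cost is one programmed column.

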8.2.4.1. Overview of Planned Adverse Event Analyses

Table 12 provides an overview of the planned adverse event safety analyses.

Table 12 Overview of Planned Adverse Event Safety Analyses

	Absolute						
Parameter	Summa	ary	Individual				
	Т	F	F	L			
AESIs & PhRMA SPERT Adverse Event Analys	es						
Analysis of AESIs	Y	Y					
Analysis of Common (\geq 5%) AEs	Y	Y					
Adverse Events							
All AEs by System Organ Class (SOC) and	v			v			
Preferred Term	I			I			
All AEs by System Organ Class (SOC) and	v						
Preferred Term (subjects and occurrences)	I						
All AEs by SOC and Preferred Term by	Y						

200807

		Absolut	.e	
Parameter	Summ	nary	Indiv	idual
	Т	F	F	L
Subgroups				
All AEs by Overall Frequency	Y			
Common AEs by Overall Frequency	Y	Y1		
All AEs by Maximum Intensity	Y			
All Drug-Related AEs by Maximum Intensity	Y			
All Drug-Related AEs by SOC and Preferred Term	Y			
Common Non-Serious AEs by SOC and Preferred Term (subjects and occurrences)	Y			
Subject Numbers for Individual AEs				Y
Relationship Between AE SOCs, Preferred Term & Verbatim Text				Y
Serious and Other Significant Adverse Events				
SAEs by SOC and Preferred Term (subjects and occurrences)	Y			
SAEs by Maximum Intensity	Y			
Reasons for Considering as a SAE				Y
Drug-Related SAEs by SOC and Preferred Term (subjects and occurrences)	Y			
Fatal SAEs by SOC and Preferred Term (subjects and occurrences)	Y			Y
Non-Fatal SAEs by SOC and Preferred Term (subjects and occurrences)	Y			Y
Drug-Related Fatal SAEs by SOC and Preferred Term (subjects and occurrences)	Y			
AEs Leading to Permanent Discontinuation of Randomized Treatment by SOC and Preferred Term	Y			Y
BP Exacerbation Events	Y			
BP Exacerbation SAEs	Y			
Other Significant AEs				Y
Other CV Events				
Other CV Events ²				

NOTES:

• T = Table, F = Figure, L = Listing, Y = Yes display generated.

• Summary = Represents TFL related to any summaries (i.e. descriptive statistics) of the observed raw data.

• Individual = Represents FL related to any displays of individual subject observed raw data.

[1]: Plot of common AEs and relative risk will be generated.

[2]: Electronically generated patient profiles will be produced and used in the preparation of SAE summaries as a part of the study report.

8.2.4.2. Planned Adverse Event Safety Statistical Analyses

AESIs & PhRMA SPERT Adverse Event Analyses

Adverse events of special interest are described in Section 10.6.4.

Summaries of AESIs will include the number, percentage and rate per 100 person-years of subjects having at least one occurrence, the number of events, the number of subjects by number of occurrence, the characteristics of the AE (serious, drug-related, etc.), outcome, maximum intensity, time to first onset/worsening, and action taken summarized by treatment group. For each count, a subject will be summarized as follows:

- Serious/drug-related/severe/fatal: If any specific AE falls in the respective category, the subject will be counted in that category.
- Outcome: The subject will be counted within a category if there is at least one specific AE in that category.
- Maximum intensity: The specific AE with the maximum intensity will be counted for this purpose. For example, a subject will be counted in the 'severe' category if there is at least one specific AE with severe intensity. A subject will be counted in the 'moderate' category if there is at least one specific AE with moderate intensity and there is no specific AE with severe intensity.
- Time to first onset/worsening (days): The earliest of onset dates for the specific AE treatment start + 1

If the AE onset date/AE worsening and/or resolution date is missing or incomplete in the database for any occurrence of the specific AE, time to first onset/worsening will be left missing for the subject. These summaries of special interest AEs will be provided for those AEs classified as treatment emergent.

Cumulative incidence function (CIF) plots may be produced for each AESI summarizing the time to first occurrence of the AESI by treatment group. If there are less than 20 subjects total for both the daprodustat and rhEPO arm, then these plots will not be created. Competing risks for the AESI cumulative incidence plots include:

AE of Special Interest (Event of interest)	Competing Risk Events
Thrombosis and/or tissue ischemia secondary	Death due to any cause prior to the AESI
to excessive erythropoiesis	
Cardiomyopathy	Death due to any cause prior to the AESI
Pulmonary artery hypertension	Death due to any cause prior to the AESI
Cancer-related mortality and tumor progression	All other non-cancer-related death prior to the
and recurrence	AESI (use death date as the competing risk
	date)
Esophageal and gastric erosions	Death due to any cause prior to the AESI
Proliferative retinopathy, macular edema,	Death due to any cause prior to the AESI
choroidal neovascularization	
Exacerbation of rheumatoid arthritis	Death due to any cause prior to the AESI
Worsening of hypertension	Death due to any cause prior to the AESI

Additionally, as a part of the PhRMA SPERT analyses described in Section 8.2.4, treatment emergent AE of special interest are considered Tier 1 events. The relative risk, corresponding two-sided 95% confidence intervals and two-sided p-values comparing daprodustat vs. rhEPO for these Tier 1 AEs will be provided.

200807

The number, percentage and rate per 100 person-years for subjects reporting Tier 2 AEs will be summarized by system organ class, preferred term and treatment group. Additionally, as a part of the PhRMA SPERT analyses described in Section 8.2.4, the most common treatment emergent AEs that are not Tier 1 AEs are considered to be Tier 2 AEs. The relative risk will be calculated for these Tier 2 AEs and a corresponding two-sided 95% confidence interval comparing daprodustat vs. rhEPO. Two two-sided p-values will be displayed: one that makes no adjustment for multiplicity and one that makes the double FDR adjustment.

Dot plots displaying the incidence of the event will be provided for the Tier 1 and Tier 2 events by AESI term (Tier 1)/ preferred term (Tier 2) and treatment group. The incidence rate in each treatment group and corresponding two-sided 95% confidence interval for the relative risk of the daprodustat group compared to the rhEPO group will be provided.

Adverse Events

The number and percentage of subjects reporting at least one AE will be provided for each treatment group. These events will be summarized by treatment group, primary system organ class, and preferred term. Pre-treatment and treatment emergent AEs will be summarized separately.

The number and percentage of subjects and the number of occurrences of all treatment emergent AEs will be summarized by primary system organ class, and preferred term.

Summaries of all treatment emergent AEs will be produced for the age group, gender, race group, baseline dialysis type, weight quartile subgroups. Summaries of treatment emergent AEs by subgroup will be produced twice: by system organ class and preferred term and separately by overall frequency.

A listing of AE records for all subjects who reported AEs will be produced.

Summaries of all treatment emergent AEs will be provided by maximum intensity. For AEs reported more than once by a subject, the most severe intensity will be included in summaries where applicable. The max intensity will be presented as "Unknown" if Missing and/or N/A are the only available severity values. Analysis will be repeated for all drug-related treatment emergent AEs.

The number and percentage of subjects reporting the most common treatment emergent AEs (those occurring in \geq 5% of subjects in any treatment group) will be summarized by preferred term and treatment group.

The number and percentage of subjects reporting treatment emergent AEs assessed by the investigator to be related to the study drug will be summarized by treatment group, primary system organ class, and preferred term and separately by overall frequency.

The number and percentage of subjects and the number of occurrences of common nonserious treatment emergent adverse events (those occurring in \geq 5% of subjects in any treatment group) will be summarized by primary system organ class, preferred term, and treatment group and separately by overall frequency.

200807

A listing of which subjects reported specific adverse events will be produced.

The hierarchical relationship between MedDRA SOCs, PTs and verbatim text will be listed for all adverse events.

Serious and Other Significant Adverse Events

The number and percentage of subjects and the number of occurrences of treatment emergent SAEs will be provided for each treatment group. These events will be summarized by treatment group, primary system organ class, and preferred term. Treatment emergent SAE preferred terms will also be summarized by treatment group and overall frequency.

Summaries of treatment emergent SAEs will be provided by maximum intensity.

A listing of reasons for considering as a SAE will be produced for all treatment emergent SAEs.

The number and percentage of subjects and the number of occurrences of treatment emergent drug-related SAEs, fatal SAEs, non-fatal SAEs, and drug-related fatal SAEs will be summarized by treatment group: by primary system organ class and preferred term and separately by overall frequency.

A listing of treatment emergent fatal SAE records and a listing of treatment emergent non-fatal SAE records will be provided.

The number and percentage of subjects reporting treatment emergent AEs leading to discontinuation of randomized treatment will be summarized by treatment group, primary system organ class, and preferred term.

A listing of treatment emergent AEs leading to discontinuation of randomized treatment will be provided.

BP events and BP-related SAEs are defined in Section 10.6.4.

The number and percentage of subjects with at least one on-treatment BP event will be provided for each treatment group. In addition, this summary will include the number and percentage of subjects with at least one on-treatment BP event that is considered clinically significant and the number and percentage of subjects with at least one ontreatment BP event that is considered to be symptomatic.

The number and percentage of subjects reporting at least one treatment emergent BPrelated SAE will be provided for each treatment group. In addition, the number of treatment emergent BP-related SAEs will be summarized by treatment group, primary system organ class, and preferred term.

A listing of other significant adverse events will be produced. Other significant adverse events are events that are not reported as fatal or serious but represent ICH-defined 'Other significant adverse events' (i.e., marked haematological and other laboratory

200807

abnormalities and any adverse events that led to an intervention, including withdrawal of drug treatment, dose reduction, or significant additional concomitant therapy). For this study, other significant AEs will be defined as non-fatal non-serious AEs resulting in an action taken with study treatment of either 'dose interrupted/delayed' or 'dose reduced'.

Other CV Events

GSK has identified other CV events of interest for all clinical studies. In this study, investigators will be required to fill out the specific CV event page of the eCRF for the following CV AEs and SAEs or any event that may potentially be one of the categories listed:

- Arrhythmias
- Pulmonary hypertension
- Valvulopathy
- Revascularization

Electronically generated patient profiles for subjects reporting these events will not be prospectively created.

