 Post-Randomization last contact date for censoring (subjects not having AE) will be defined as the study completion date. 	
 Treatment emergent last contact date for censoring (subjects not having AE) will be defined as follows: 	
 1 day after the last non-zero dose date (last non-zero dose date + 1) for subjects not having treatment emergent AE and continuing on study past (last non-zero dose date + 1) 	
 Last non-zero dose date for all other subjects 	
AE Patient Years: (Cumulative total of time to AE for subjects who have the AE +	

200807

Advers	se Events
	Cumulative total of censoring time for subjects without the AE) / 365.25
	 For treatment emergent AEs, the start date of the patient years value for each subject should be the treatment start date.
	 For post-randomization AEs, the start date of the patient years value for each subject should be the randomization date.
	 For follow-up AEs, the start date of the patient years value for each subject should be 2 days after the last non-zero dose date (last non-zero dose date + 2).
•	Incidence Rate (per 100 patient years): (100 * Number of subjects with at least 1 AE) / AE person years
٠	For the analysis of the time to AE onset/worsening, if the AE onset/worsening date is missing then the time to AE onset/worsening will be counted as 1 day.
10.6.4	.4. Laboratory Parameters

Laboratory Parameters

•	If a laboratory value which is expected to have a numeric value for summary purposes, has a non-detectable level reported in the database, where the numeric value is missing, but typically a character value starting with ' <x' '="" or="">x' (or indicated as less than x or greater than x in the comment field) is present, the number of significant digits in the observed values will be used to determine how much to add or subtract in order to impute the corresponding numeric value. • Example 1: 2 Significant Digits = '< x' becomes $x - 0.01$ • Example 2: 1 Significant Digit = '> x' becomes $x + 0.1$ • Example 3: 0 Significant Digits = '< x' becomes $x - 1$</x'>
•	If there is more than one laboratory value on the same date for the same laboratory test, then the laboratory values associated with scheduled visits will be used. Hgb summaries and analyses are an exception and should use the data handling conventions outlined in Section 10.6.3.

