10.7.2.1. Handling of Missing and Partial Dates

Element	Reporting Detail				
General	Partial dates will be displayed as captured in subject listing displays.				
Concomitant Medications	 Partial dates for any concomitant medications recorded in the CRF will be imputed using the following convention: 				
	 If the partial date is a start date, a '01' will be used for the day and 'Jan' will be used for the month 				
	 If the partial date is a stop date, a '28/29/30/31' will be used for the day (dependent on the month and year) and 'Dec' will be used for the month. 				
	 The recorded partial date will be displayed in listings. 				
Adverse Events	• The eCRF allows for the possibility of partial dates (i.e., only month and year or only year) to be recorded for AE start/worsening and end dates. In such a case, the following conventions will be applied for calculating the time to onset and the duration of the event:				

Element	Reporting Detail				
	 Imputing a Start/Worsening Date from a Partial Start/Worsening Date: 				
	 If an imputed worsening date is before the start date, then the start 				
	date will be used as the imputed worsening date.				
	 Completely missing stop date: 				
	If only the day is missing, the first of the month will be used				
	unless the Screen Week -8 visit date, Run-In visit date or				
	treatment start date also occurs in the same month.				
	 If the treatment start date occurs in the same month, then the treatment start date will be used as the start/worsening date. 				
	Otherwise, if the Run-In visit date occurs in the				
	same month (and the treatment start date is not in that month), then the Run-In visit date will be used as the start/worsening date.				
	• Otherwise, if the Screen Week -8 visit date occurs in the same month (and the treatment start and Run-In visit dates are not in that month), then the Screen Week -8 visit date will be used as the				
	start/worsening date.				
	If the day and month are missing, then '01' will be used for the day and 'Jan' will be used for the month unless the Screen Week -8 visit date, Run-In visit date or treatment start date also occurs in the same year.				
	 If the treatment start date occurs in the same year, then the treatment start date will be used as the start/worsening date. 				
	 Otherwise, if the Run-In visit date occurs in the same year (and the treatment start date is not in that year), then the Run-In visit date will be used as the start/worsening date. 				

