	If only the day is missing, the last day of the month will be					
	used unless the treatment stop date also occurs in the					
	same month; in this case the treatment stop date will be					
	used at the stop date.					
	 If the day and month are missing, then '31' will be used for 					
	the day and 'Dec' will be used for the month, unless the					
	stop date of study treatment also occurs in the same year;					
	in this case the study treatment stop date will be used as					
	the stop date.					
	 Latest of (start date and latest worsening date) is partial or non- 					
	missing and is after treatment stop date:					
	If only the day is missing, the last day of the month will be					
	used unless the study conclusion date also occurs in the					
	same month; in this case, the study conclusion date will be					
	used as the stop date.					
	 If the day and month are missing, then '31' will be used for 					
	the day and 'Dec' will be used for the month, unless the					
	study conclusion date also occurs in the same year; in this					
	case, the study conclusion date will be used as the stop					

Element	Reporting Detail				
	date.				
	• Completely missing start, worsening or end dates will remain missing, with no imputation applied. Consequently, time to onset and duration of such events will be missing.				
CV Safety Endpoint Events	Discussed in Section 10.6.4				

200807

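### A missing resolution date blanks the AESI time to first onset, and the SAP's rules for missing AE onset dates conflict

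*SAP*

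**What the plan says.** Three sections of the SAP govern time to AE onset when dates are missing.

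- **Section 8.2.4.2 (AESI summaries).** Time to first onset/worsening is defined by "The earliest of onset dates for the specific AE treatment start + 1"; the minus sign before treatment start appears to have been lost in the text. The exception begins "If the AE onset date/AE worsening and/or resolution date is missing or incomplete in the database for any occurrence of the specific AE", and its consequence is "time to first onset/worsening will be left missing for the subject".
- **Section 10.6.4.3 (general AE definitions, beside the person-years and incidence-rate formulas).** For the time-to-onset analysis, "if the AE onset/worsening date is missing then the time to AE onset/worsening will be counted as 1 day".
- **Section 10.7.2.1 (missing and partial dates).** For partial AE dates, "the following conventions will be applied for calculating the time to onset and the duration of the event". For the rest, "Completely missing start, worsening or end dates will remain missing, with no imputation applied". The stated result is "Consequently, time to onset and duration of such events will be missing".

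No section says which rule takes precedence.

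**The concern.** There are two problems. First, a date that plays no part in time to onset can erase it, and one such date on any occurrence is enough to erase it for the subject. Second, the three sections give different answers for the same record when the onset date is partial or absent.

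At stake are the AESI time-to-first-onset summary and, for events with no onset date, the person-time in the AESI rates per 100 person-years. Two programmers following the SAP could produce different values from one database.

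**Working it through.** No figure in the plan can be reproduced here, so the check sets the rules side by side.

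| Record | 8.2.4.2 | 10.6.4.3 | 10.7.2.1 |
|---|---|---|---|
| Onset fully missing | missing | 1 day | missing |
| Onset partial | missing | not addressed | imputed, time computed |
| Onset complete, resolution missing or incomplete | missing | computable | computable |
| First occurrence day 100, resolved; second day 400, no resolution date (assumed days) | missing | day 100 | day 100 |

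**Rows 3 and 4: resolution date.** The 8.2.4.2 formula needs only the earliest onset date and treatment start. In Section 10.4.1.4 the resolution date enters duration, not time since first dose. Section 10.7.2.1 also has a branch for a completely missing stop date, which imputes a partial start date. It therefore expects time to onset to be obtainable when no stop date exists, whereas 8.2.4.2 blanks it. In row 4 the first onset is fully dated and resolved, and it is still lost because of the later occurrence.

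**Row 2: partial onset.** Section 10.7.2.1 imputes the date expressly so that time to onset can be calculated. Section 8.2.4.2 sets that time to missing because the recorded date is incomplete.

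**Row 1: fully missing onset.** Sections 10.6.4.3 and 10.7.2.1 are both general AE rules for the same quantity, and they disagree.

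**Consequence of row 1 for the rates.** Section 8.2.4.2 asks for AESI rates per 100 person-years. Section 10.6.4.3 defines these as

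rate = 100 × subjects with at least one AE / AE person-years,

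AE person-years = (sum of times to AE + sum of censoring times) / 365.25.

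Under Section 10.4.1.4, an AE with no onset date is treatment emergent if its resolution date is missing or falls on or after treatment start. A subject whose only AESI record is of this kind stays in the numerator. That subject adds 1 / 365.25 = 0.0027 years to the denominator under 10.6.4.3, and an undefined amount under 10.7.2.1. A known onset with a missing resolution date causes no difficulty here, because the rate formula does not use resolution.

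**The case against.** **Ongoing events may not be caught.** A reader might infer that the rule removes every subject with an ongoing AESI, leaving only resolved events and biasing the comparison between arms. The SAP does not support that. It does not say how an ongoing AE is stored, Section 10.7.2 defines missing as requested data not provided, and it does not count a not-applicable answer as missing. If no resolution date is requested for an unresolved event, the rule may not touch it. What remains is that 8.2.4.2 makes no exception for ongoing events, so a blank field would be caught on a literal reading. No share of affected subjects, and no direction by arm, can be derived from the document.

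**The sections may serve different outputs.** Section 8.2.4.2 can be read as an AESI-specific override of the partial-date convention. The 1-day rule sits beside the rate formulas, where a time is needed. This softens the partial-date conflict, although the SAP states no such precedence. It does not explain the resolution-date condition or reconcile 10.6.4.3 with 10.7.2.1. Section 10.7.2.1 describes partial dates as month and year or year only, and nothing suggests that fully missing onsets are common.

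**The 1-day rule.** A reader might say it creates false early events. It does not; it assigns a time to an event already reported.

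**The any-occurrence condition.** This is defensible for onset dates. If one occurrence is undated it may be the earliest, and ignoring it could present a later dated occurrence as the first. This objection stands and limits the fix.

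**Conclusion.** The point holds in limited form. The resolution-date condition in 8.2.4.2 is a wrong rule rather than missing detail, because followed as written it discards onset times that are known. The conflict between 10.6.4.3 and 10.7.2.1 on fully missing onset dates is real, and it remains even if 8.2.4.2 is read as an override. The partial-date conflict should be settled with it.

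The reach is narrow. The certain effect is on one descriptive item, AESI time to first onset/worsening. The rates per 100 person-years are exposed only to the conflict over fully missing onset dates. The cumulative incidence plots are optional, and nothing says they inherit the 8.2.4.2 rule; they would be affected only if programmed from the same variable. AESI counts, percentages, CMH tests and relative risks do not need these times. The co-primary and principal secondary analyses are not involved.

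The conclusion rests on the literal text. The number of subjects affected depends on how resolution dates are recorded for unresolved events, which the SAP does not state.

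**What to change.** 1. In Section 8.2.4.2, remove the resolution date from the condition, so that time to first onset/worsening depends only on onset/worsening dates and treatment start.
2. State there that partial onset/worsening dates are imputed as in Section 10.7.2.1.
3. State one rule for fully missing onset/worsening dates and use it in Sections 8.2.4.2, 10.6.4.3 and 10.7.2.1. It should say what time such an event contributes to AE person-years.
4. Keep the any-occurrence condition for fully missing onset dates, unless the rule in step 3 says how to handle a subject with one undated occurrence among dated ones.

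The cost is a few lines of SAP text and matching programming specifications. No new data are needed. The one risk is dropping the any-occurrence condition outright, which step 4 avoids.
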